#### 6.1 6. Study methods

#### **Description of randomisation**

Randomisation will be carried out after eligibility has been confirmed and consent given, and baseline measurements have been made. Randomisation will be performed by an authorised member of the local research team using a secure internet-based randomisation system ensuring allocation concealment. Participants will be randomised in a 2:1:1 ratio to: i) high resistance IMT ii) low resistance IMT or iii) usual care (no IMT and written instructions on deep breathing exercises). The random allocation will be stratified by centre and specialty, so that each speciality at each centre will have approximately equal numbers of participants allocated to the high resistance IMT group and low resistance IMT group/usual care. As the study is not evaluating the surgery per-se, surgical experience is not a criterion for participation (all participants will be under the care of a consultant surgeon). In the context of this study, clustering by surgeon is not relevant to the sample size and can be ignored (on the basis that the intraclass correlation is negligible; personal communication with [name] for a previous study).

In the SWAT (section 5.2), participants in the high resistance IMT group will be randomised in a 1:1:1:1 ratio to one of the four groups with random allocation stratified by centre and specialty.

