| EQ-5D-5L  | ✓                                   |   |  | ✓               |                |           | ✓                            | ✓                            |
| MUST & PONS assessments   |                                     |   |  | ✓               |                |           |                              |                              |
| DASI questionnaire  | ✓                                   |   |  |                 |                |           |                              | ✓                            |
| HADS, CDRQ & self-
efficacy
questionnaires                                  | 4                                   |   |  |                 |                |           |                              | *                     |
| Surgical regret questionnaire   |                                     |   |  |                 |                |           |                              | ✓                            |
| Adverse events  |                                     |   | ✓  | ✓               | ✓              | ✓         |                              |                              |
| Serious adverse events  |                                     |   | ✓  | ✓               |                |           | ✓                            | ✓                            |

\* High resistance IMT/low resistance IMT training can be at POA appointment if more than 2 weeks before surgery. An additional visit will need to be booked if POA appointment is less than 2 weeks before surgery.

6.7

Abbreviation guide: CDRQ: Connor Davidson Resilience Questionnaire; CPET: cardiopulmonary exercise testing; DASI (Duke Activity Status Index); HADS: Hospital Anxiety and Depression Scale; IMT: inspiratory muscle training; MIP: maximal inspiratory pressure; MUST: Malnutrition Universal Screening Tool; PONS: Perioperative Nutrition Screen; POA: pre-operative assessment; PPCs: postoperative pulmonary complications.

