#### Overview

Serious and other adverse events (AEs) will be recorded and reported in accordance with GCP guidelines and BTC (CTEU)'s Serious Adverse Events and Safety Reporting Standard Operating Procedure (SOP-GE-012) (see Figure 2).

[figure not shown]
INSPIRE Protocol Version 2.0 As there are no known long term safety concerns associated with using IMT, and any adverse events associated with IMT can only occur whilst the participant is undertaking IMT, safety reporting to the Sponsor will take place only while the participant is exposed to the intervention. In practice this means that the SAE reporting period will commence at the training session and continue until the patient is admitted to hospital for their index procedure. SAEs may be identified by ad hoc reporting from the patient, data collection at the extra training visits (where applicable) or on admission to hospital.

The complications or side effects of IMT, i.e. 'expected events' may include: dyspnoea, headache, pain, cough, nausea, chest discomfort, tachycardia, bradycardia, syncope, hypertension, bronchospasm, dizziness, syncope, epistaxis, respiratory distress, respiratory failure, perforated eardrum, cephalalgia. Any other event will be considered 'unexpected'. It is worth noting that the 'expected events' are events considered in other RCTs of IMT, but none of the RCTs have reported differences in the rate of any of these events between IMT/non-IMT groups, therefore these events may be regarded as hypothetical.

All unexpected and fatal SAEs will be reported to the coordinating centre, who will check the report and then forward to the Sponsor. Reporting to the Sponsor will occur within 24 hours of the site team becoming aware of the event. If the event is ongoing at the time of initial reporting the participant will be actively followed up and a follow-up report will be provided within 5 days of the initial report. Further follow up reports will be submitted only when there has been a significant change/update of the SAE until the SAE has resolved, or a decision for no further follow-up has been taken by the local PI.

All AEs during the participant's hospital stay and SAEs after hospital discharge will be recorded in detail on a CRF. At the conclusion of the study, all AEs recorded during the study will be subject to statistical analysis, and the analysis and subsequent conclusions will be included in the final study report.

Figure 2 Serious adverse event reporting flow chart

9.3

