#### Additional 'virtual' follow up meeting vs no additional 'virtual' follow up meeting

i) One additional 'virtual' follow up meeting

Participants in the high resistance IMT group will receive an additional follow up meeting conducted via telephone or video call within one week of the initial IMT training session (ideally day 3 to 5). The research nurse or physiotherapist will assess adherence and progression of the training load and will provide further training or support where it is required (section 5.6.3). Participants will have been provided with and may have watched a step-by-step digital recording (video) on how to use the device at the initial IMT training session and will have also been provided with written information, a paper training diary for recording training sessions, and telephone support in the form of a helpline number that participants can call (if they have any queries or require assistance). Within the training diary they will be asked to rate their perceived exertion using the RPE rating scale after each training session.

ii) No additional 'virtual' follow up meeting

Participants will attend the initial IMT training session with a research nurse or physiotherapist but participants will not receive an additional virtual follow up meeting.

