## SWAT sample size

It is planned to recruit 160 participants to the high intensity IMT during Phase 1; 40 per each of the four treatment combinations. The SWAT will provide 95% confidence intervals of width +/- 0.31 standard deviations in progression of training load for the main effects of visit and method load adjustment and 95% confidence intervals of width +/- 0.45 standard deviations for comparisons between load method when an extra visit is included and separately between load method when an extra visit is not included.

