#### 3.2 Data sources

Outcome data will be collected using a purpose-designed database. Where the trial database is the site of original recording this will be considered source data. Data will be captured at several timepoints including screening, from admission for surgery to discharge and followed-up for up to 6 months.

Where the database isn't the original recording the source data will include, but is not limited to medical history, medication records, vital signs, physical examination records, and questionnaire responses.

Table 2 Data collection schedule

Data item	Baseline (Pre- randomisation)	Initial training visit* High/low resistance IMT/usual care groups	Additional virtual follow up High resistance IMT group: Phase 1 only	Pre- surgery	In hospital	Discharge	3 months post- surgery	6 months post- surgery
Socio-demographic details	✓							
Co-morbidities	✓							
Routine CPET parameters#				✓				

Maximal inspiratory pressure (MIP)		✓		✓				
Spirometry		✓		✓				
Check on adherence and progression of the IMT training load §			~	4				
Routine clinical measures	✓	✓		✓	✓	✓		
PPCs					✓	✓	✓	✓
Resource use schedule					✓	✓	*	✓
SF-12	✓			✓			✓	✓
EQ-5D-5L	✓			✓			✓	✓
MUST & PONS assessments				✓				
DASI questionnaire	✓							✓
HADS, CDRQ & self- efficacy questionnaires	*							✓
Surgical regret questionnaire								✓
Adverse events			✓	✓	✓	✓		
Serious adverse events			✓	✓			4	✓

\* High resistance IMT/low resistance IMT training can be at POA appointment if more than 2 weeks before surgery. An additional visit will need to be booked if POA appointment is less than 2 weeks before surgery.

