## Statistical Analysis Plan Inspire IRAS Ref: 250345

Randomised patients									
(n=XX)			Intensity (Unanticipated events only)						
Event			Unlikely to	Possibly	Probably	Definitely			
Patients	% 	Not related	be related	related	related	related	Mild	Moderate	Severe

Table of events (excluding relatedness and intensity) to be repeated with participants grouped by treatment received

Table A15: Serious adverse events reported throughout the trial

	Randomised patients (n=XX)		Relatedness						Intensity (Unanticipated events only)		
	Event Patients	, % 	Not related	Unlikely to be related	Possibly related	Probably related	Definitely related	Mild	Moderate	Severe	
Any anticipated event											
Infective											
Cardiovascular											
GI											
Respiratory/pulmonary											
Nervous system / Neurological / Psychiatric											
Immune system											
Metabolism / Nutrition											
Eye											
Ear / Labyrinth											
Hepatobiliary											

	Randomised patients (n=XX)				Intensity (Unantisinated events only)					
	Event		Relatedness Unlikely to Possibly			Probably	Definitely	Intensity (Unanticipated events only		
	Patients	% 	Not related	be related	related	related	related	Mild	Moderate	Severe
Renal / Urinary										
Reproductive / Breast										
·										
Skin / Subcutaneous tissue										
Musculoskeletal / Connective tissue / bone										
General										
Anatomical / Surgical dam										
Oncology										
Investigations										
Injury										
Re-operation										
ке-орегация										
Chemo / Radiotherapy										
Any event not anticipated										

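### Adverse events during training have one extra scheduled collection point in half of the high resistance arm and none in the comparators, which may bias that arm's recorded rate upward; the SAP neither adjusts for this nor mentions it

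*Protocol*

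**What the plan says.** Protocol section 9.2 (Overview of safety reporting) treats events caused by IMT as possible only while the participant is training. For that window it says: "SAEs may be identified by ad hoc reporting from the patient, data collection at the extra training visits (where applicable) or on admission to hospital".

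Protocol Table 3 and SAP Table 2 both tick AEs and SAEs at the additional contact. The SAP column is headed "Additional virtual follow up High resistance IMT group: Phase 1 only". Low resistance IMT and usual care have no matching column. Both tables also tick AEs and SAEs at pre-surgery, with no restriction by arm.

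The contact is one factor of the 2x2 study within a trial (SWAT). Protocol 6.1 states that "participants in the high resistance IMT group will be randomised in a 1:1:1:1 ratio to one of the four groups", and two of the four cells (AV, MV) have the contact. On numbers, the SAP says: "It is planned to recruit 160 participants to the high intensity IMT during Phase 1; 40 per each of the four treatment combinations". On timing, SAP 2.1.2 says: "Participants in the high resistance IMT group will receive an additional follow up meeting conducted via telephone or video call within one week" (ideally day 3 to 5). Protocol 6.4 sets training at a minimum of 2 weeks and up to 8.

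SAP 1.1.2 records that the study closed at the end of Phase 1. SAP 3.3.3 groups the safety population by treatment received. SAP 4.5.4 says that AEs and SAEs collected throughout the trial will be tabulated. The last shell table is "Table A15: Serious adverse events reported throughout the trial". Nothing in the SAP separates events by collection point or warns of unequal ascertainment.

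**The concern.** A fair comparison of harms needs the arms to be observed with equal intensity. Here half of one arm has a scheduled collection point within a week of starting. Everyone else's first scheduled collection is pre-surgery, at least 2 and up to 8 weeks after starting. The contact is made by a research nurse or physiotherapist, and Protocol 6.2 says that staff administering IMT are not blind to allocation.

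The imbalance falls in the window that the protocol regards as relevant to IMT harm. Several of the expected events listed in section 9.2 (headache, cough, nausea, dizziness) can be mild and easily forgotten weeks later. In a small, truncated trial whose harms are read descriptively, one or two additional recorded events in the arm under test can colour the safety conclusion.

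**Working it through.** **1. Share of the arm with the contact.** Two of four equal cells is s = 80/160 = 0.50. The plan's own SWAT precision confirms the split. The half-width for 80 v 80 is 1.96 × √(2/80) = 0.310 SD (0.312 with the t distribution), against a stated 0.31. For 40 v 40 it is 1.96 × √(2/40) = 0.438 (0.445 with t), against a stated 0.45. Under 2:1:1 allocation, 160 high resistance participants correspond to about 160 comparators, none with the contact. These are planned numbers; the documents do not give the final recruitment.

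**2. Model.** Suppose the true event rate is equal in all arms. Let
- q = chance that an event is recorded through routes open to all arms (ad hoc report, pre-surgery or admission);
- f = share of training-period events that arise before the contact;
- e = chance that the contact picks up an event which would otherwise be missed.

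Then the recorded ratio, high resistance to comparator, is

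1 + s·f·e·(1 − q)/q.

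The documents give none of q, f or e, so all three are assumptions. I take e = 0.9 throughout.

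**3. Results with s = 0.5.**

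| Timing assumed | f | s·f·e | q = 0.8 | q = 0.6 | q = 0.4 |
|---|---|---|---|---|---|
| Half of events before the contact | 0.500 | 0.225 | 1.06 | 1.15 | 1.34 |
| Contact on day 5 of 14, events evenly spread | 0.357 | 0.161 | 1.04 | 1.11 | 1.24 |
| Contact on day 7 of 56, events evenly spread | 0.125 | 0.056 | 1.01 | 1.04 | 1.08 |

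Example: 1 + 0.225 × 0.6/0.4 = 1.34. With q = 1 every entry is 1.00.

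**4. SAEs.** If the common routes catch 90%, the three rows give 1 + 0.225 × 0.1/0.9 = 1.025, then 1.018 and 1.006.

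**5. In events.** With 160 high resistance participants, an assumed true rate of 10% and f = 5/14, the excess is 160 × 0.10 × 0.161 × (1 − q). That is 0.3 events at q = 0.9 and 1.3 at q = 0.5.

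**6. Effect of early closure.** At the planned 1,250 high resistance participants, with the contact confined to Phase 1, s would have been 80/1250 = 6.4%. With f = 5/14, e = 0.9 and q = 0.5 the ratio would have been 1.02, against 1.16 with s = 0.5.

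**7. Effect of the fix.** Using only high resistance participants without the contact sets s = 0, and the ratio returns to 1.00 for any q, f and e.

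**The case against.** A reader might infer that the high resistance arm's rates are higher by construction. The documents do not support that. Every arm has AE and SAE collection at pre-surgery, and ad hoc reporting and admission are listed as routes without restriction by arm. Only events that those routes miss can add to the count.

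A reader might also infer that participants are actively asked about harms at the contact. The quoted sentence covers SAEs only. The descriptions of the contact (Protocol 5.2.2 and 5.6.3.2, SAP 2.1.2) mention adherence, load, technique and support. Collection of AEs there rests on the schedule ticks.

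Nor does it follow that a real excess could not be told apart from the artefact. The contact is itself randomised, so AV/MV against AN/MN shows the ascertainment effect directly, although with limited precision.

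Three further points reduce the stakes and stand:
- SAP 4.4.3 models only the two primary outcomes. Harms are tabulated, and no harm ratio or test is specified.
- Tables A13 and A14 cover the index admission and the 3 and 6 month follow-up, so no shell table is dedicated to non-serious training-period AEs. Table A15 spans the trial but is for SAEs only, and no note to repeat it by treatment is visible.
- SAEs by definition involve death, threat to life, hospitalisation or lasting disability, and are hard to miss at admission.

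Finally, the quoted safety text is from protocol version 2.0, with a face-to-face visit, while the SAP follows version 3.0, with a virtual meeting. Version 3.0 is not among the documents. The imbalance appears in both schedules.

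What remains is that SAP 3.3.3 and 4.5.4 allow a by-treatment display of events from the whole trial, without any safeguard against this imbalance.

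**Conclusion.** The point holds as a potential bias that should be handled in the harms reporting. Training-period ascertainment is more intensive by design in about half of the analysed high resistance arm, and this feature can only raise that arm's recorded rate relative to the others or leave it unchanged.

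The size is uncertain because it turns on what the common routes miss. The ratio is 1.00 if they miss nothing, and roughly 1.01 to 1.34 for recall of 80% down to 40% over the timings in the table. The top of that range needs both poor recall and half of all events before the contact. It could apply to mild, transient AEs but not plausibly to SAEs, for which the effect is probably negligible. Early closure matters because Phase 2 participants will not dilute the share with the contact.

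**What to change.** In SAP 4.5.4, and for any by-treatment display that includes training-period events (Table A15 among them):

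1. Add a by-arm tabulation of AN and MN participants against low resistance IMT and usual care. It needs only allocations already held. Define it by randomised allocation, so that the comparison stays randomised; SAP 3.3.3 otherwise groups by treatment received.
2. Where the case report form identifies the collection point, list events known only from the additional contact separately. Keep ad hoc and admission reports in the comparison, since both are open to all arms. The documents do not say whether the collection point is recoverable, and it is too late to start recording it: closure was confirmed in May 2022 and the SAP is dated July 2024.
3. Footnote the unequal ascertainment. The same footnote can mention that Protocol 5.6.5 gives helpline numbers to both IMT groups and does not state this for usual care; restricting to AN and MN does not remove that smaller difference.

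The cost is some SAP wording and one further display. Restricting to AN and MN halves the high resistance sample there (80 of 160 planned), so it should sit beside the full tabulation and not replace it.

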
#### Period for recording serious adverse events

Data on SAEs will be collected for each participant from the start of their training session until the end of their 6 month follow-up period or withdrawal from the study. SAE reporting to the Sponsor will only occur during the period when participants are exposed to the intervention.

10.1

## 10. Ethical considerations

#### Review by an NHS Research Ethics Committee

The study will comply with the Declaration of Helsinki (http://www.wma.net/) on research involving human subjects. The study protocol, PIL and consent form and any subsequent amendments to these documents, will be submitted to the Sponsor, Health Research Authority (HRA), and an NHS REC for approval. All participating sites will need to confirm capability and capacity to deliver the protocol. The study will be conducted in accordance with the GCP guidelines, UK Data Protection Act 2018 and the UK Policy Framework for Health and Social Care Research. Any amendments to these documents, after a favourable opinion from the REC has been given, will be submitted to the REC and / or HRA for approval prior to implementation.

## Patient and Public Involvement (PPI)

The patient, carer and public involvement and engagement (PCPIE) support group from the Royal College of Anaesthetists reviewed the proposal and will provide ongoing support. We will continue to use this group as well as the cardiac surgery PPI group established at the Bristol Cardiovascular National Institute for Health Research (NIHR) Biomedical Research Unit (BRC) 10.2 and the perioperative medicine PPI group established at the University Hospital Southampton NIHR BRC. Patient and Public Involvement (PPI) input is crucial to the success of the study and will provide invaluable input (particularly during Phase 1) which will feed into how patients will be approached and recruited to the study, and how the information about the different interventions will be presented to them.

## Risks and anticipated benefits

IMT is a safe intervention; all RCTs assessing the safety and efficacy of IMT in surgical populations that reported the incidence of adverse events caused by IMT, reported that there were no adverse events [12].

The main benefit to participants is the anticipated reduction in PPCs and the potential for quicker recovery after surgery. The main potential benefit to society is improved patient experience of surgery and post-operative recovery, which can lead to quicker discharge from hospital and therefore improve efficiency and flow through the healthcare system.

## 11. Research governance

This study will be conducted in accordance with:

- Good Clinical Practice (GCP) guidelines
- UK Policy Framework for Health and Social Care

11.1

## **Sponsor approval**

The study protocol and other study documents will be submitted to the Sponsor for sponsor assessment prior to submission to the regulatory authorities. Any changes to the protocol will be reviewed by the funder. The TSC and funder will also be invited to review and approve any other amendments to the study documents prior to submission to the HRA/REC or other regulatory authorities.

### **NHS** approval

Confirmation of capability and capacity from the local NHS Trust is required prior to the start of the study at each site.

Any amendments to the study documents approved by the HRA/REC will be submitted to participating sites for either (i) review of ongoing capacity and capability or (ii) notification only.

## Investigators' responsibilities

Investigators will be required to ensure that local research processes have been followed and that any contractual agreements required have been signed off by all parties before recruiting any participant. Investigators will be required to ensure compliance to the protocol and study manual and with completion of the CRFs. Investigators will be required to allow access to study 11.3 documentation or source data on request for monitoring visits and audits performed by the Sponsor or BTC (CTEU) or any regulatory authorities.

Investigators will be required to read, acknowledge and inform their study team of any amendments to the study documents approved by the HRA/REC that they receive and ensure that the changes are complied with.

